5.1.3 Physical Examination

Physical examinations will be performed according to the Schedule of Visits and Assessments (Section 1.3). The physical exam will be limited to skin, lungs and heart only.

5.1.4 Vital Signs, Height and Weight

Vital signs will be performed according to the Schedule of Visits and Assessments (Section 1.3). Weight, blood pressure, heart rate, and temperature will be collected in seated position after 5 mins. Subjects will be instructed to void prior to weight being taken and to remove any objects of significant weight (i.e., jackets, outerwear, shoes, cell phones, wallet, key chains, etc.).

Height will be measured at Baseline (Day 1) only.

5.1.5 12-lead ECGs

12-lead ECGs will be performed according to the Schedule of Visits and Assessments (Section 1.3).

ECGs will be obtained on subjects after 5 minutes in the supine position. All ECG tracings and readouts will be reviewed by the Investigator and central reader at the ECG laboratory.

5.1.6 Laboratory Tests

All tests listed in Table 3 below will be performed according to the Schedule of Visits and Assessments (Section 1.3) unless otherwise noted. The collection of specimens will be in a non-fasting state (no food restrictions). In addition, laboratory safety tests may be performed at various unscheduled time points, if deemed necessary by the Investigator.

Table 3. Laboratory Tests

Hematology	Serum Chemistry

 • Hemoglobin • Hematocrit • Total and differential leukocyte count • Red blood cell count with indices and morphology • Platelet count • Reticulocyte count¹ 	
 • Blood Urea Nitrogen • Bilirubin (total and direct) • Alkaline phosphatase • Aspartate aminotransferase • Alanine aminotransferase • Albumin • Sodium • Potassium • Chloride • Glucose • Creatinine • Creatine kinase
Urinalysis	Additional Tests

 • pH • Specific gravity • Protein² • Glucose • Ketones • Bilirubin • Blood² • Nitrite² • Urobilinogen • Leukocyte esterase² 	
 • Thyroid Stimulating Hormone T4 (TSH/T4) • Urine pregnancy test³ (for females of childbearing potential only) • Serum pregnancy test (hCG)⁴ • Follicle-stimulating Hormone (FSH) ⁵ • Pharmacokinetic (PK) assessments

¹ If red blood cell count, hemoglobin or hematocrit values are below the lower limit of normal, reticulocyte count will be performed

² If urinalysis is positive for protein, blood, nitrite and/or leukocyte esterase, a microscopic examination (for red blood cells, white blood cells, bacteria, casts, and epithelial cells) will be performed.

³ Cohort 1: At Baseline, Day 8, Day 15 and Day 22 for FOCBP only. Cohort 2: At Baseline, Week 4, 8, 12 and 13 for FOCBP only.

⁴ At screening only for FOCBP.

⁵ If indicated to confirm post-menopausal status

5.1.7 Local Tolerability Assessment

The Investigator Local Tolerability Assessment will be performed according to the Schedule of Visits and Assessments ([Section 1.3](#)).

Application site reactions will be graded at the timepoints outlined in the Schedule of Visits and Assessments ([Section 1.3](#)). Irritation reactions are graded using the scale detailed in the following section ([Berger 1982](#)). **Reactions at the site of product application, which may occur post-Baseline, should be differentiated from the preexisting inflammation associated with the subject's chronic hand eczema.**

The Investigator assessments will be conducted by the Investigator prior to investigational product application in the clinic.

Dermal Response

- 0 = no evidence of irritation
- 1 = minimal erythema, barely perceptible
- 2 = definite erythema, readily visible; minimal edema or minimal papular response
- 3 = erythema and papules
- 4 = definite edema
- 5 = erythema, edema and papules
- 6 = vesicular eruption
- 7 = strong reaction spreading beyond application site

Other Effects

- A = slight glazed appearance
- B = marked glazing
- C = glazing with peeling and cracking
- D = glazing with fissures
- E = film of dried serous exudates
- F = small petechial erosions and/or scabs
- G = no other effects

The Subject Local Tolerability Assessment will be performed according to the Schedule of Visits and Assessments ([Section 1.3](#)).

This assessment will be administered by the site 10 to 15 minutes after investigational product application in the clinic.

Grade	Sensation Following Investigational Product Application
0 (none)	No sensation
1 (mild)	Slight warm, tingling sensation; not really bothersome
2 (moderate)	Definite warm, tingling sensation that is somewhat bothersome
3 (severe)	Hot, tingling/stinging sensation that has caused definite discomfort

5.1.8 Adverse Events

Adverse events (AEs) will be collected continuously during the study beginning at informed consent and assessed according to the Schedule of Visits and Assessment ([Section 1.3](#)).

Any treatment emergent AEs will be followed in the clinic for up to one month at the Investigator's discretion until resolved or otherwise judged as clinically stable.

For further details on Adverse Events please see [Section 5.7](#).

5.2 Efficacy Evaluations

5.2.1 Investigator's Global Assessment (IGA)

Investigator's Global Assessment of chronic hand eczema will be performed according to the Schedule of Visits and Assessments ([Section 1.3](#)).

The IGA is a static evaluation of qualitative overall chronic hand eczema severity. This global assessment scale is an ordinal scale with five severity grades (reported only in integers of 0 to 4). Each IGA Severity Score is defined by distinct and clinically relevant morphologic descriptions that minimizes inter-observer variability.

Every effort must be made for the same Evaluator to complete the IGA for the subject at every study visit.

IGA will be assessed at clinic visits prior to the subject applying Investigational Product and other physician assessments.

Investigator Global Assessment of Disease (IGA)

Score	Grade	Description
0	Clear	Absence of erythema and scaling, AND
		Absence of vesiculation, edema, and fissures. Note: Post-inflammatory pigmentary changes may be present.
1	Almost clear	Barely perceptible or faint erythema, and/or Slight flaking over limited areas, mostly fine scales, AND
		Absence of vesiculation, edema, or fissures
2	Mild	Barely perceptible or faint erythema, and/or Slight flaking over limited areas, mostly fine scales AND
		Scattered vesicles affecting up to 10% of hand, without erosion, and/or Dermal swelling over less than 10% of hands, and/or
		Cracked skin affecting a small area of the hand
3	Moderate	Either barely perceptible or faint erythema, or prominent redness, and/or Either slight flaking over limited areas, mostly fine scales, or flaking over widespread area(s), coarser scale AND
		Scattered or clustered vesicles affecting up to 30% of hand, without visible erosion or excoriation, and/or Definite dermal swelling over more than 10% of hand, and/or
		Cracked skin affecting multiple areas of the hand
4	Severe	Either prominent or deep intense red color, and/or Either flaking over widespread area(s), coarser scales, or desquamation covering over 30% of the hand, with coarse thick scales AND
		At least one of the following: High density of vesicles extending over large area(s), or with erosion or excoriation, and/or
		Dermal swelling with skin induration over widespread area(s), and/or One or more deep fissures and causing bleeding

Adapted from [Ruzicka 2008](#).

5.2.2 Body Surface Area (BSA)

BSA Assessments will be performed according to the Schedule of Visits and Assessments (Section 1.3).

The BSA affected by chronic hand eczema will be determined by the subject's hand method, where the subject's hand (including fingers) surface area is assumed to equal 1% of body surface area (BSA). Lesions on both hands will be added together. Affected areas of the lateral aspects of the fingers and hands should be assigned to the palmar surface.

5.2.3 Worst Itch Numerical Rating Scale (WI-NRS)

Subjects will complete the WI-NRS pruritus assessment. WI-NRS Assessments will be performed according to the Schedule of Visits and Assessments (Section 1.3).

Subjects will complete the WI-NRS pruritus assessment in the clinic during Screening and then daily at home from the Baseline/Day 1 visit until the last visit. Subjects will record their WI-NRS on a diary and will return the diary to the clinic at each visit. Sites will review WI-NRS entries and enter into the CRF.

The WI-NRS has been developed as a simple, single item to assess the patient-reported severity of this symptom at its highest intensity during the previous 24-hour period. (Naegeli 2015). The WI-NRS will be determined by asking the subject's assessment of worst itch over the past 24 hours. The scale is from '0 to 10' ("no itch" to "worst imaginable itch").

ITCH NUMERIC RATING SCALE

Please rate your itching severity by circling the number that best describes your worst level of itching in the past 24 hours.

0 1 2 3 4 5 6 7 8 9 10

0 = No itch

10 = Worst itch
imaginable

[figure not shown]
Copyright © (2017) Eli Lilly and Company. All rights reserved.

5.2.4 NRS-Pain Scale

The Numerical Rating Scale (NRS) for Pain will be performed according to the Schedule of Visits and Assessments (Section 1.3).

Subjects will complete the NRS Pain assessment in the clinic during screening and then daily at home from the Baseline/Day 1 visit until the last visit. Subjects will record their NRS-Pain score on a diary and will return the diary to the clinic at each visit. Sites will review NRS-Pain entries and enter into the CRF.

The NRS-Pain Scale is the most widely used instrument for pain screening. Subjects will select the number between 0 and 10 that fits best to their worst pain intensity over the past 24 hours, where 0 represents ‘no pain at all’ and 10 ‘the worst pain possible’.

Source: https://www.physio-pedia.com/images/4/47/NRS_pain.jpg

5.2.5 HECSI

The Hand Eczema Severity Index (HECSI) will be performed according to the Schedule of Visits and Assessments (Section 1.3).

HECSI is an instrument used in clinical trials to rate the severity of 6 clinical signs of hand eczema and the extent of the lesions on each of 5 hand areas by use of standard scales. The total HECSI score is based on a 4-point severity scale ranging from 0 (none/absent) to 3 (severe) and a 5-point scale rating the affected area(s) ranging from 0 (0% affected area) to 4 (76% to 100% affected area).

Clinical Signs	Fingertips	Fingers (except tips)	Palm of hands	Back of hands	Wrists
Erythema (E)					
Infiltration/papulation (I)					
Vesicles (V)					
Fissures (F)					
Scaling (S)					
Oedema (O)					
SUM (E + I + V + F + S + O)					
Extent (Ex)					
Total HECSI Score =	Sum x Ex +	Sum x Ex +	Sum x Ex +	Sum x Ex +	Sum x Ex +

Total HECSI score (min 0; max 360). For each location (total of both hands) the affected area was given a score from 0 to 4: (0, 0%; 1, 1-25%; 2, 26-50%; 3, 51-75%; 4, 76-100%) for the extent of clinical symptoms. Finally the score given for the extent for each location was multiplied by the total sum of the intensity of each clinical feature (each contributing equally to the final score) and the total sum called the HECSI score was calculated, varying from 0 to a maximum severity score of 360 points.

Adapted from [Held 2005](#).

5.2.6 Quality of Life in Hand Eczema Questionnaire

The Quality Of Life in Hand Eczema Questionnaire (QOLHEQ) will be performed according to the Schedule of Visits and Assessments ([Section 1.3](#)) in Phase 2b (Cohort 2). The QOLHEQ is an instrument to assess disease specific Health Related Quality of Life (HRQOL) in patients suffering from hand eczema ([Appendix 1](#)). The construct HRQOL includes all impairments or limiting conditions caused by the health state of an individual. The QOLHEQ is a disease specific instrument, thereby only assessing impairments caused by hand eczema. It consists out of 30 items which can be summarized according to four domains of HRQOL: Impairments because of (1) symptoms, (2) emotions, (3) limitations in functioning or (4) because of treatment and prevention.

5.2.7 Nail Dystrophy Assessment

Phase 2b (Cohort 2)

A Nail Dystrophy Assessment will be performed in Cohort 2 according to the Schedule of Visits and Assessments ([Section 1.3](#)) to identify any alteration of nail morphology. Assessment to include the following evaluations by the Investigator:

Baseline/Day 1:

- Does the subject have at least one nail with significant dystrophy extending to the cuticle? Yes/No
- If “Yes”, record which nail has the worst dystrophy (indicating left or right)

Subsequent visits according to the Schedule of Visits and Assessments:

- For the identified fingernail with the worst dystrophy at Baseline/Day 1, is there normal appearing nail distal to the cuticle, Yes/No
- If “Yes”, how many millimeters of normal appearing nail distal to the cuticle?

Sites participating in optional photography will obtain photos of nail with the worst dystrophy at Baseline/Day 1 and at subsequent visits according to the Schedule of Visits and Assessments ([Section 1.3](#)) and [Section 5.3.2](#).

5.3 Other Evaluations

5.3.1 Pharmacokinetics Assessment

PK draws will be performed according to the Schedule of Visits and Assessments ([Section 1.3](#)) for all subjects at all sites.

Phase 1 (Cohort 1)

- Serial PK sampling will be performed on Day 1 (1, 2, 4, 6, and 24 hours post-dose administration), and at Day 15 (pre-dose and 1, 2, 4, 6, and 24 hours post-dose administration). For 24-hour timepoints, subjects return to the clinic on the following day

within 2 hours of the IP application time from the previous day for PK plasma sample collection. A pre-dose/trough PK sample will be taken at Day 8.

Phase 2b (Cohort 2):

- PK will be evaluated through trough/pre-dose sampling at Baseline, Day 29, and Day 85.

PK draws will be collected while the subject is having serum chemistries drawn at applicable visits. The draws will be pre-dose investigational product application in the clinic. Ensure investigational product is not applied in the area where PK will be drawn.

5.3.2 Medical Photography

Phase 2b (Cohort 2)

Photography will be performed at selected investigational sites using Canfield photography equipment according to the Schedule of Visits and Assessment ([Section 1.3](#)) in Phase 2b (Cohort 2). Photography will be optional. All efforts will be made to de-identify the subjects.

Sites participating in optional photography will obtain photos of nail with the worst dystrophy at Baseline/Day 1 and at subsequent visits according to the Schedule of Visits and Assessments ([Section 1.3](#)).

5.4 Final Study Visit – End of Study

Phase 1 (Cohort 1)

The approximate final study visit will occur at Week 3 (Day 22).

Phase 2b (Cohort 2):

The approximate final study visit will occur at Week 13 (Day 92).

For both Cohorts, the procedures performed during these visits are as described in the Schedule of Visits and Assessments ([Section 1.3](#)). A 3-day scheduling window is allowed for this visit. Adverse events will be recorded as reported by the subject and followed to resolution (as necessary).

5.5 Early Termination Visit

If a subject is withdrawn or wishes to exit the study prior to the final study visit, an early termination visit will be scheduled. This visit should include the procedures and assessments that would be performed at the final study visit for either Cohort 1 or Cohort 2 ([Section 1.3](#)).

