- ^l Any emergent AEs will be followed in the clinic for up to 1 month at the Investigator's discretion until resolved or otherwise judged as clinically stable

B. Cohort 2 (Phase 2b)

Study Procedure	Screen	Baseline Day 1	Wk 2 Day 15	Wk 4 Day 29	Wk 8 Day 57	Wk 12 Day 85	Wk 13 Day 92
Visit	1	2	3	4	5	6	7
Visit Window	-4 weeks		+/- 3 days	+/- 5 days	+/- 5 days	+/- 7 days	+/- 3 days
Informed consent	X						
Demographics	X						
Medical and surgical history	X						
Physical examination ^a	X	X				X	
Vital signs, height, weight ^b	X	X	X	X	X	X	X
I/E criteria	X	X					
Randomization		X					
Hematology, Serum Chemistries, UA, TSH/T4 ^c	X	X		X	X	X	
Resting 12-lead ECG	X			X		X	
BSA, IGA, HECSI ^d	X	X	X	X	X	X	X
NRS pain, WI-NRS ^e	X	Completed daily from Day 1 to Week 13 Visit 					
QOLHEQ ^e	X	X	X	X	X	X	X
Nail dystrophy assessment ^f		X	X	X	X	X	X
Local Tolerability Assessments ^g		X	X	X	X	X	
Optional Photography ^h		X	X	X	X	X	X
Urine pregnancy test ⁱ		X		X	X	X	X
Serum pregnancy test ⁱ	X						
Follicle-Stimulating Hormone (FSH) ^j	X						
PK sampling ^k		X		X		X	
IP application/Subject training in clinic ^l		X	X	X	X	X	
Dispense IP kit ^m		X	X	X	X	X	
Dispense/review diary		X	X	X	X	X	
Weigh IP tubes ⁿ		X	X	X	X	X	
Compliance calculation ^o		X	X	X	X	X	
Adverse event assessment ^p	X	X	X	X	X	X	X
Concomitant medications	X	X	X	X	X	X	X

Footnotes from above table:

- ^a Limited physical examination: skin, lungs, and heart only
- ^b Height will be collected at Visit 2 (Baseline/Day 1) only. Weight will be collected at Baseline, Weeks 4, 8 and 12.
- ^c If Baseline visit occurs within 14 days of Screening, the Screening lab results may be utilized.
- ^d BSA will be measured as the affected BSA for each side of each hand. Affected areas of the lateral aspects of the fingers and hands should be assigned to the palmar surface. IGA will be a 5-point scale ranging from clear (0) to severe (4). **IGA should be completed prior to other physician assessments and by the same Evaluator at each study visit.** HECSI is an instrument used in clinical trials to rate the severity of 6 clinical signs of hand eczema and the extent of the lesions on each of 5 distinct hand anatomic areas by use of standard scales. The total HECSI score is based on a 4-point clinical sign severity scale ranging from 0 (none/absent) to 3 (severe) and a 5-point scale rating the different affected hand anatomic area(s) ranging from 0 (0% affected area) to 4 (76% to 100% affected area).

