4.10 Treatment Stopping Rules

If a subject has non-cutaneous adverse events of concern, clinically significant laboratory values or any condition that the Investigator determines could possibly be related to the investigational product, the Investigator should immediately contact the Medical Monitor to discuss if the subject should be discontinued from treatment with investigational product.

Treatment for any individual subject will be discontinued if the subject experiences:

- A serious adverse event (SAE) or a clinically significant non-serious AE which in the opinion of the Principal Investigator or Medical Monitor warrants discontinuation from the study for that subject's well-being.
- A treatment-emergent severe (Grade 3 or higher) laboratory abnormality (confirmed by repeat sample).
- A severe infection (Grade 3 or higher)
- An Ischemic or thromboembolic cardiovascular event (regardless of Grade)
- Any other adverse event that represents an unacceptable risk to the subject (e.g., Grade 3 or higher)

As noted above, study treatment must be discontinued immediately in the event of a female subject's pregnancy.

Treatment should be interrupted:

- If a subject develops an application site reaction with the clinical appearance of an 'irritation reaction', and with a severity of a Dermal Response Score of 5 (erythema, edema and papules) or greater on the scale of Berger and Bowman, treatment should be interrupted for up to one week and may then be resumed if the reaction has, in the opinion of the Investigator, adequately resolved.

Treatment should be discontinued:

- If the application site reaction reoccurs, treatment should be discontinued permanently, and the subject followed until the reaction resolves.

For cases of suspected allergic contact dermatitis, the Medical Monitor and Sponsor should be notified and there should be discussion about performing patch testing to further evaluate. Patch testing is encouraged in such cases.

Phase 2b (Cohort 2)

In the event of a medical emergency where unblinding is required to provide medical care to the subject, refer to the most current IRT plan and Breaking Treatment Codes ([Section 4.6.1](#)). Contact the Medical Monitor and the Sponsor promptly.

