### 6.1.5. Analysis Visit Windows

#### 6.1.5.1. Non-Diary Assessments

Visits will be analyzed as scheduled (i.e., not subject to visit windowing). Unscheduled, early termination, and/or repeated measurements will only be included if a scheduled measurement is not available and the unscheduled, early termination, or repeated measurement falls within the analysis visit windows as described in Table 3 (Cohort 1 [Phase 1]) and Table 4 (Cohort 2 [Phase 2b]). The windows follow the Schedule of Events in Table 1 and Table 2. Visits falling outside of these windows will not be windowed (e.g., an unscheduled visit before first application of study drug). Unscheduled/repeated measurements will be listed.

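### A Cohort 2 subject who leaves before Week 12 has no safety labs, ECG, physical examination or local tolerability score required at exit, because the early termination visit copies Week 13

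*Protocol*

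**What the plan says.** Protocol section 5.5 covers a subject who is withdrawn or chooses to exit before the final visit. It sets the content of the early termination visit in one sentence: "This visit should include the procedures and assessments that would be performed at the final study visit for either Cohort 1 or Cohort 2". Section 5.4 places the Cohort 2 final visit at Week 13, nominally Day 92.

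In the Cohort 2 schedule (section 1.3 B, repeated as SAP Table 2), four safety rows have no mark in the Week 13 column:

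- the laboratory row, "Hematology, Serum Chemistries, UA, TSH/T4"
- "Resting 12-lead ECG"
- the physical examination, footnoted as "Limited physical examination: skin, lungs, and heart only"
- "Local Tolerability Assessments"

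Week 13 does carry vital signs, BSA, IGA, HECSI, QOLHEQ, the nail assessment, a urine pregnancy test, adverse events and concomitant medications.

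Section 2.4.2 lists the monitoring that the protocol regards as adequate to protect subjects, and that list includes all four missing items. On the analysis side, SAP 6.1.5.1 states: "Unscheduled, early termination, and/or repeated measurements will only be included if a scheduled measurement is not available", provided the measurement falls in the analysis window.

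**The concern.** Leaving these items out of Week 13 is sensible for a completer, who had them a week earlier. Section 5.5 then carries the same short list over to subjects who never reached Week 12. For them, the visit on which the omission relies did not take place.

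Two things are at stake. First, several of the risks named in section 2.4.2 (neutropenia, anemia, and liver, thyroid, creatinine and creatine phosphokinase changes) can be silent and are found by laboratory test. A subject who leaves with such a change and no symptoms need not be tested. Second, the post-baseline laboratory, ECG, physical examination and tolerability summaries will hold little or nothing from early leavers. The SAP has a rule for using early termination measurements, but for these four items required collection supplies none.

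**Working it through.** The plan states no figure on this point, so the check is a reading of the schedule followed by simple counts.

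**1. Schedule rows, Cohort 2 (Protocol 1.3 B).**

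| Assessment | Scheduled at | Week 13 |
|---|---|---|
| Hematology, chemistry, urinalysis, TSH/T4 | Screening, Baseline, Weeks 4, 8, 12 | no |
| ECG | Screening, Weeks 4, 12 | no |
| Physical examination | Screening, Baseline, Week 12 | no |
| Local tolerability | Baseline, Weeks 2, 4, 8, 12 | no |
| Vital signs | every visit | yes |
| Urine pregnancy test | Baseline, Weeks 4, 8, 12, 13 | yes |
| Adverse events, concomitant medications | every visit | yes |

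**2. Last required result for an early leaver, on nominal days (Week 4 = Day 29, Week 8 = Day 57, Week 12 = Day 85).**

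| Exit | Labs | ECG | Physical examination | Tolerability |
|---|---|---|---|---|
| Before Week 4 | Baseline (Screening results may serve if within 14 days) | Screening | Baseline | Baseline or Week 2 |
| Week 4 to before Week 8 | Week 4 | Week 4 | Baseline | Week 4 |
| Week 8 to before Week 12 | Week 8 | Week 4 | Baseline | Week 8 |

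For an exit just before Day 85, the last labs are up to 85 − 57 = 28 days old, the last ECG up to 85 − 29 = 56 days, and the last physical examination up to 85 − 1 = 84 days.

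**3. How many subjects.** The protocol allows for 10% dropout in 215 subjects: 215 × 0.10 = 21.5. By arm, the allowance is 61 − 55 = 6 in each of the two 0.3% arms and 31 − 28 = 3 in each of the three smaller arms (applying the vehicle arms' allowance to the 0.1% arm of the same size). That gives 2 × 6 + 3 × 3 = 21.

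This is a ceiling for exit visits. Someone lost to follow-up attends no early termination visit, and someone who leaves between Weeks 12 and 13 has already had the tests. The documents do not give the split. Let f be the assumed share of dropouts who leave before Week 12 and do attend an exit visit. The count is then 21 × f: 21 at f = 1, about 10 at f = 0.5, about 5 at f = 0.25.

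**4. Against section 2.4.2.** Its list has nine items: physical examinations, application site reaction assessments, hematology, serum chemistry, TSH, T4, urinalysis, ECG and adverse event questioning. At the Cohort 2 exit visit only the last of these is scheduled.

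**5. Against Cohort 1.** The Day 22 final visit includes labs and a physical examination, but no ECG and no local tolerability. The same sentence in 5.5 therefore gives the two cohorts different exit content, and neither gets the full set.

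**The case against.** The protocol has several safeguards, and they count. Section 5.1 allows additional safety evaluations at discretion. Section 5.1.6 allows laboratory safety tests at unscheduled times. Section 5.6 allows unscheduled visits for any reason the Investigator finds warranted. Section 4.8 requires an adverse event that stops product to be followed until it resolves or stabilizes, and section 5.7.4 follows known events and clinically significant laboratory values for up to a month after treatment. Together these narrow the gap to abnormalities that nobody suspects. They do not close it, because discretion needs a prompt and follow-up needs a finding.

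Some stronger readings are tempting but go further than the documents do:

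- **That the subjects affected are those most likely to have a safety problem.** Stopping product (4.8) is separate from leaving the study (4.9), and adverse events are not in the 4.9 list. A subject who stops product but stays in the study keeps the Week 4, 8 and 12 tests. Some leavers may still have left because of an event: 4.10 mentions discontinuation from the study, and the SAP disposition table has Adverse Event as a reason. How many is not stated.
- **That early leavers face longer gaps than others.** The 28-day and 56-day figures are the ordinary on-treatment intervals. What differs is that no Week 12 test closes them.
- **That unscheduled visits have the same hole**, because 5.6 does not list the score in the interruption rule of 4.10 ("with a severity of a Dermal Response Score of 5 (erythema, edema and papules) or greater"). The 5.6 list is what is collected for everyone, not an upper limit, and the rule in 4.10 cannot be applied without scoring the reaction.
- **That the SAP contradicts the protocol.** The rule in 6.1.5.1 is general, and the exit visit does supply IGA, HECSI, BSA, QOLHEQ and vital signs for it to use.

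**Conclusion.** The gap is real and modest: it should be fixed, but it does not threaten the trial. Read together, Protocol 5.5, 5.4 and 1.3 B require none of the four safety assessments at exit for a Cohort 2 subject who leaves before Week 12, and no other section adds them. The size is at most about 21 of 215 subjects, or about 6 in a 61-subject arm. This rests on the 10% sample-size allowance as a guide to actual dropout; the true number of exit visits affected is lower by an amount the documents do not give.

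The primary endpoint is untouched, since IGA is collected at exit. Safety is analyzed descriptively (SAP section 9), so no test is affected. The effect is an unsuspected abnormality that may go unseen, and safety tables that under-represent early leavers. A reader might infer that the exit visit has no safety content at all; that would be wrong, since vital signs, adverse event questioning, concomitant medications and a urine pregnancy test are done.

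**What to change.** Reconcile section 5.5 with 1.3 B and 2.4.2. State that a Cohort 2 subject who exits before Week 12 has the safety assessments already scheduled at Week 12 (hematology, chemistry, urinalysis, TSH/T4, ECG, limited physical examination, local tolerability) in addition to the Week 13 procedures. Add an early termination column to the Cohort 2 schedule, and to SAP Table 2, so that sites and programmers work from the same list.

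One detail needs a sentence. The Investigator tolerability score is taken before an in-clinic application, but the subject's rating is taken 10 to 15 minutes after one. The text should say how the subject's part is handled when no product is applied at the exit visit.

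No SAP rule has to change: 6.1.5.1 already accepts early termination measurements that fall in a window. The cost is amendment wording, a slightly longer exit visit, and up to about 20 extra lab panels and ECGs using tests already in the trial. The change cannot help subjects who are lost to follow-up. It should be made early, because exit results that were not collected cannot be recovered later.
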